### *Secondary Outcome Measures:*

- Postoperative return to everyday activities. Time required for returning to everyday activities. Measurement unit: days [Time Frame: Maximum time frame 50 days postoperatively]
- Postoperative pain level. Pain level after surgery, quantified with the use of the VAS scale. [Time Frame: 7, 14, 21, 28, 35, 42 and 49 days postoperatively]
- Postoperative analgesics consumption. Number of analgesic pills consumed per day after surgery. Measurement unit: pills per day [Time Frame: 7, 14, 21, 28, 35, 42 and 49 days postoperatively]
- Overall satisfaction level. Satisfaction level measured at a 0-10 scale [Time Frame: 50 days postoperatively]
- Cost of the material. Overall cost of the dressings applied [Time Frame: Maximum time frame 50 days postoperatively]
- Wound care visits. Number of required visits for postoperative wound care for each patient per week.[Time Frame: 7, 14, 21, 28, 35, 42 and 49 days postoperatively]
- Trauma secretions. Trauma secretions leading to extra dressing care. If such an episode occurs, then it will be defined as=1 'YES' If such an episode does not occur,

then it will be defined as=0 'NO' [Time Frame: 7, 14, 21, 28, 35, 42 and 49 days postoperatively]

- Wound contamination. Contamination of the wound trauma. If such an episode occurs, then it will be defined as=1 'YES' If such an episode does not occur, then it will be defined as=0 'NO' [Time Frame: Maximum time frame 50 days postoperatively]
- Wound erythema. Erythema of the wound. If such an episode occurs, then it will be defined as=1 'YES' If such an episode does not occur, then it will be defined as=0 'NO' [Time Frame: Maximum time frame 50 days postoperatively]
- Wound hematoma. Hematoma of the wound. If such an episode occurs, then it will be defined as=1 'YES' If such an episode does not occur, then it will be defined as=0 'NO' [Time Frame: Maximum time frame 50 days postoperatively]
- Disease recurrence. Disease recurrence rate. If such an episode occurs, then it will be defined as=1 'YES' If such an episode does not occur, then it will be defined as=0 'NO' [Time Frame: Maximum time frame 1 year postoperatively]
- Difference in the quality of life of the patient. Difference in the quality of life of the patient based on the Quality of Life with Chronic Wounds Wounds (Qol) Questionnaire [Time Frame: 7, 14 and 21 days postoperatively]
- Medium term quality of life. Quality of life of the patient based on the Short Form 36 (SF-36) questionnaire [Time Frame: 28 days postoperatively]
- Treatment satisfaction. Patient satisfaction regarding the treatment results measured at a 1-5 scale [Time Frame: 35 days postoperatively]
- Treatment acceptance. Patient acceptance regarding the re-application of the treatment measured at a 1-5 scale [Time Frame: 35 days postoperatively]

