### OBJECTIVE

The current study aims at comparing two groups of patients that will be subjected to surgical resection of pilonidal cyst and secondary intention wound healing. In the first group, dressings like alginate cord with silver and high G cellulose will be used for filling of the wound cavity and a hydrocapillary dressing for sealing and waterproofing the wound. In the other group, simple gauze dressings for the coverage of the wound cavity will be used. Comparison of the two groups will involve all the endpoints that indicate whether such dressings can facilitate faster wound healing, enabling, thus, patients to faster return to their everyday activities. Furthermore, a parameter that has not been, previously, studied, the quality of life after the surgical excision of the pilonidal cyst, by using the SF – 36 and the Quality of life with Chronic Wound questionnaire, will, also, be investigated.

# CHAPTER 3

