## MATERIALS AND METHODS

### **1. Estimation of the necessary study sample size**

According to literature, the mean time required for wound healing of patients subjected to pilonidal cyst resection is  $60.4 \pm 6.2$  days. Therefore for a 5% decrease in the duration of the healing process and with an 1:1 enrollment ratio between the two groups, with alpha 0,05 and 90% power, the required number of patients in each group is 89. The total amount of patients required for completion of the study is 178. Patients that will not complete follow-up will be excluded and replaced by other patients.

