### **10. The questionnaires used for evaluation of the patients quality of life**

#### **participating in this study.**

Two questionnaires will be used, SF-36 and Quality of life with Chronic Wound. The first one will be the Greek version of the questionnaire and the second one will be in the original English version and will be answered by patients that have the necessary knowledge of the English language. SF-36 will be answered from the patients every four weeks. Quality of life with Chronic Wound will be answered every seven days by phone or during reevaluation.

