### **11. Consent Form.**

Every patient will sign preoperatively a consent form agreeing to participate in the study after being informed.

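### SF-36 is fixed at day 28 with no preoperative score planned, so the comparison gives up precision that one cheap baseline form would supply

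*Protocol*

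**What the plan says.** Section 7 of the protocol lists the SF-36 as one secondary endpoint at one time: "Quality of life of the patient based on the Short Form 36 (SF-36) questionnaire [Time Frame: 28 days postoperatively". Section 10 describes its administration differently: "SF-36 will be answered from the patients every four weeks". It gives neither a first nor a last administration.

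The Objective describes the aim as "the quality of life after the surgical excision of the pilonidal cyst, by using the SF – 36", together with the chronic-wound questionnaire. The Introduction says that postoperative quality of life will receive emphasis. The chronic-wound questionnaire is also collected only after surgery: "Questionnaire [Time Frame: 7, 14 and 21 days postoperatively".

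Two preoperative steps involving the patient's entry into the trial are described. One is consent: "Every patient will sign preoperatively a consent form agreeing to participate in the study after being informed" (section 11). The other is the opening of the allocation envelope as the patient enters the operating room (section 5). Neither mentions a questionnaire.

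Section 10 also says that the SF-36 is given in Greek, while the chronic-wound questionnaire is given in English to patients who know the language. The SF-36 is therefore the only quality-of-life instrument not restricted by language.

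**The concern.** A patient's general health before surgery usually predicts general health four weeks later. If it is measured, an adjusted comparison removes the predictable part of the between-patient spread. If it is not measured, that part stays in the residual variance unless other covariates capture it. Eligibility is broad (ages 18 to 80, ASA I to IV, all disease stages), so preoperative scores will plausibly vary a good deal.

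The timing of data collection has to be settled in the protocol. A statistical analysis plan can choose the model, but it cannot recover a preoperative score that was never collected. Without that score, the report also cannot describe how day-28 quality of life compares with the patient's state before surgery, or show whether the arms started level on the SF-36.

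**Working it through.** **The plan's own figure.** Section 1 of Materials and Methods gives a healing time of 60.4 days (SD 6.2), "for a 5% decrease in the duration of the healing process" and "with alpha 0,05 and 90% power", with 1:1 allocation and 89 per group.

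- Difference: 0.05 × 60.4 = 3.02 days.
- n per group = 2 × (1.960 + 1.282)² × (6.2 / 3.02)² = 2 × 10.51 × 4.215 = 88.6, rounded up to 89.

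The stated 89 reproduces with a two-sided test (power 0.901). A one-sided test would give 73. This figure concerns healing time. The protocol states no target difference, SD or power for the SF-36, so 89 per arm enters below only as the available sample size.

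**SF-36 at day 28 without a baseline.** In units of the SD of the day-28 score:

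- Standard error = √(2/89) = 0.150 SD.
- Detectable difference at 90% power = (1.960 + 1.282) × 0.150 = 0.49 SD.
- Detectable difference at 80% power = (1.960 + 0.842) × 0.150 = 0.42 SD.

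**SF-36 at day 28 adjusted for a preoperative score.** With correlation r between the preoperative and day-28 scores, analysis of covariance multiplies the variance by 1 − r² and the detectable difference by √(1 − r²). The sample size that gives the same precision without adjustment is 89 / (1 − r²). The documents do not give r, so a range is assumed.

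| Assumed r | Variance remaining | Variance cut | Detectable, 90% power | Detectable, 80% power | Equivalent n per arm, unadjusted |
|---|---|---|---|---|---|
| 0 (no baseline) | 1.00 | 0% | 0.49 SD | 0.42 SD | 89 |
| 0.3 | 0.91 | 9% | 0.46 SD | 0.40 SD | 98 |
| 0.5 | 0.75 | 25% | 0.42 SD | 0.36 SD | 119 |
| 0.7 | 0.51 | 49% | 0.35 SD | 0.30 SD | 175 |

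**Adjustment, not change scores.** If the SD is the same at both times, the variance of a change score relative to the day-28 score alone is 2(1 − r): 1.4 at r = 0.3, 1.0 at r = 0.5 and 0.6 at r = 0.7. Below r = 0.5 a change score would be worse than no baseline at all. At each of these values the adjusted comparison has the smaller variance (0.91, 0.75, 0.51).

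**The two schedule statements side by side.** Counted from surgery, a four-weekly schedule gives day 28 and then day 56. Section 7 uses only day 28, and day 56 lies beyond the 50-day limit that applies to every endpoint except recurrence. Counted from time 0, the schedule would include a preoperative form, but section 10 does not say so and section 7 lists none. The two sections do not settle which forms are collected.

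**The case against.** The strongest reply is that nothing here is invalid. The endpoint is a postoperative level, the Objective speaks of quality of life after excision, and randomisation makes the day-28 comparison unbiased. All of that stands.

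Four stronger readings are tempting, and the documents do not support them.

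- **That the protocol promises an SF-36 change it cannot compute.** A reader might infer this from the phrase "Difference in the quality of life of the patient" in section 7. That phrase belongs to the chronic-wound questionnaire at days 7, 14 and 21, not to the SF-36.
- **That all the spread from broad eligibility must fall into the error term, and that chance imbalance cannot be handled.** Age and ASA score are eligibility items and disease stage is classified under section 2, so all three are available before surgery and can be adjusted for. A preoperative SF-36 adds only what it explains beyond them. The table compares with no adjustment and so shows the most that could be gained at each r.
- **That the trial is underpowered for the SF-36.** No SF-36 target is stated, so there is no shortfall against the plan. At r = 0.3 the gain is small, from 0.49 to 0.46 SD.
- **That a baseline is definitely ruled out.** Section 10 leaves the first administration open. The absence of a preoperative score is a reading of what both sections omit. If one was intended, it needs to be written down.

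What remains is that a preoperative score is not planned in the text, cannot be recovered later, and would improve the comparison at little cost.

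**Conclusion.** The point holds as a cheap improvement of minor severity. The SF-36 endpoint is limited to day 28, the four-weekly schedule in section 10 has no stated start, and no preoperative SF-36 is planned. The consequence is lost precision and a result that is harder to interpret. It is not bias, and it affects one secondary endpoint.

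For assumed correlations of 0.3 to 0.7, the precision forgone is 9% to 49% of the variance. This is equivalent to about 9 to 86 more patients per arm in an unadjusted analysis (98 − 89 and 175 − 89). These figures rest on 89 analysed patients per arm, a two-sided 5% level, 90% power, the assumed correlation, and no other covariate adjustment. With age, ASA score and disease stage already in the model, the gain would be smaller.

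**What to change.** In sections 7 and 10, state the same SF-36 administration times, and say whether any form after day 28 is collected and used.

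Add a preoperative Greek SF-36, completed after consent and before the allocation envelope is opened. That order matters because patients are not blinded (section 6), so only a score taken before allocation is known is free of its influence.

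State that day-28 scores will be compared between arms adjusted for this baseline, rather than as change from baseline.

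The cost is one more self-completed form per patient and a few minutes of the patient's time, plus a line in each of the two sections. Section 11 says only that consent is signed before surgery and does not describe a separate visit, so the sponsor should confirm that there is time for the form between consent and entry to the operating room. No additional patients are needed.

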## **8. Experimental Group**

The pilonidal cyst will be resected, with the use of a scalpel and then hemostasis will be performed with diathermy.

Alginate dressings with silver and high-G cellulose, which combine increased absorption properties, antimicrobial action and high coherence will be used. The size of the dressings will be 3cm X 45cm and 1 cm cord will be used for filling the wound cavity. Dressings with perimetric adhesive layer from natural materials for latent breathing of the skin with dressing dimensions based on the wound size, will be also placed.

Wound care will be performed in a specific way each time that the dressings will be removed. The wound will be irrigated with normal saline and betadine solution and finally without pressure the trauma will be dried.

### **9. Active Comparator**

The pilonidal cyst will be resected, with the use of a scalpel and then hemostasis will be performed with diathermy.

Wound care will be performed with the application of simple gauze dressings. Wound care will be performed in a specific way each time that the dressings will be removed. The wound will be irrigated with normal saline and betadine solution and finally without pressure the trauma will be dried.

### **10. The questionnaires used for evaluation of the patients quality of life**

#### **participating in this study.**

Two questionnaires will be used, SF-36 and Quality of life with Chronic Wound. The first one will be the Greek version of the questionnaire and the second one will be in the original English version and will be answered by patients that have the necessary knowledge of the English language. SF-36 will be answered from the patients every four weeks. Quality of life with Chronic Wound will be answered every seven days by phone or during reevaluation.

### **11. Consent Form.**

Every patient will sign preoperatively a consent form agreeing to participate in the study after being informed.

### **12. Trial.**

The present non-commercial prospective randomized controlled study will be conducted in the Department of Surgery of the University Hospital of Larissa. Patient data will be recorded both in the patient charts and in an electronic database. The hospital will not be addressed with any form of economic burden. There will be no form of financial support for the present study.

